### **Statistical analysis**

Summary statistics for outcomes and predictor variables will be calculated, with comparisons made using Student's t-test and Wilcoxon rank-sum test for normally and non-normally distributed continuous variables, respectively. Counts and percentages will be calculated for categorical variables and compared using  $\chi^2$  or Fisher's exact test as appropriate. COVID disease status will be ascertained based on medical records review for severe hospitalized patients, self-reported history of viral illness with serological confirmation of anti-COVID status, and anti-COVID antibody status. The association between CQ and disease will be explored. Efficacy analyses included all the patients who underwent randomization and who received at least one dose of CQ or placebo (modified intention-to-treat population). The primary end point, the percentage of patients with COVID infection at study end, will be compared in the CQ group and in the placebo group with the use of a stratified Cochran–Mantel–Haenszel test, with strata corresponding to the stratification factors (age and exposure levels). To isolate the association between CQ and possible confounders we will define as those variables associated with both the outcome and the independent variable (CQ). Statistical calculations will be performed using STATA version 12. A two-tailed  $\alpha$  of 0.05 was defined as the level of statistical significance for all tests.

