NCT04349371

Title: Chloroquine (CQ) prophylaxis for Health Care Workers at risk for COVID

Short title: Saved by CQ

Clinical Phase: II

PI: [name] MPH

Co-investigator: [name] MPH

Protocol Version: 3.0 (IRB approved 11/09/2020)

**Primary Objective:** The primary objective is to determine the clinical efficacy of CQ in health care workers with moderate to high risk of exposure to COVID-19 in preventing symptomatic COVID-19 infections.

**Secondary Objectives:** Secondary endpoints will explore the efficacy of CQ in preventing any infection as defined by seroconversion to positive anti-COVID antibody status.

**Study Design:** Double blind, placebo controlled, randomized study of CQ in health care workers with risk of COVID exposure. The primary objective is to determine the clinical efficacy of CQ in health care workers with moderate to high risk of exposure to COVID-19 in preventing symptomatic COVID-19 infections. Safety assessments include AEs, vital signs, ECGs, and physical examinations.

Stratification will be based and levels of exposure: -moderate risk: defined by patient facing work in outpatient/in-house clinic at least 2 days/week -high risk: ICU/ER/procedure rooms with aerosolized particles and high risk of contamination Stratification based on age: -Under 50 years of age -Older than 50 years of age

**Sample size:** 175 patients/group. Sample size based on a projection that 15% of healthcare workers will develop symptomatic COVID-19 illness and an anticipated 67% reduction in rate (i.e. 5%) among those treated with CQ. 175 patients per group, allowing for a 10% dropout rate, will permit detection of a difference of this magnitude or greater for the primary endpoint, assuming a two-tailed alpha and 80% power. The trial is not powered on any secondary outcomes or interim analyses.

**Study Duration:** -1 month accrual of patients with treatment duration of 2-3 months or until exposure levels become negligible - 2 month follow up visit, 3 month follow up visit

**Treatment Description:** 3 Patients will receive CQ 500 mg every day for one week, then 500 mg weekly for the duration of the exposure. A dose of 250 mg daily will be allowed for severe GI intolerance.

**Primary Endpoint:** Decrease by 67% in number of symptomatic illness in at risk healthcare workers; a decrease in symptomatic COVID infections from 15% to 5% in the treatment arm.

**Co-primary Endpoint:** Decrease by 70% in number of severe illness in at risk healthcare workers.

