**Secondary Endpoints:** 1. Decrease by 67% in number of sero-conversions in at risk healthcare workers. 2. Percent of patients with adverse events NCI-CTCAE Grade 3 or higher. 3. Percent of patients with GI intolerance.

**Inclusion Criteria:** 1) Age  $\geq$ 18 years, 2) Employment by New York Presbyterian Hospital 3) Clear assignment to areas of the hospital that involve patient contact and possible exposures for at least 2 days a week  $\geq$  8 hours a day

**Exclusion Criteria:** 1) Individuals who are taking CQ for other indications 2) New use of NSAIDs 3) High risk background medications not limited to immunosuppressive regimens, steroids, anti-B cell therapies, anti-cytokine therapies, chemotherapies, JAK-inhibitors 4) Individuals with a history of retinopathy that would contraindicate the use of CQ 5) Known allergy to CQ or chloroquine 6) Known QT prolongation and torsades de point 7) Have screening electrocardiogram (ECG) abnormalities that, in the opinion of the investigator, are clinically significant and indicate an unacceptable risk for the patient's participation in the study. 8) Any individual with QTc over 500 msec will be excluded. 8) Individuals who have history of any cardiac disease. 9) Individuals with history of renal disease 10) Individuals who are taking any QT prolonging meds such as but limited to: • Antipsychotics: Haloperidol, Ziprasidone, Quetiapine, Thioridazine, Olanzapine, Risperidone • Antiarrhythmics: Amiodarone, Sotalol, Dofetilide, Procainamide, Quinidine, Flecainide • Antibiotics: Macrolides, Fluoroquinolones • Antidepressants: Amitriptyline, Imipramine, Citalopram, • Others: Methadone, Sumatriptan, Ondansetron, Cisapride

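### For non-hospitalised workers any self-reported viral illness plus positive serology can make a symptomatic case, so an unrelated illness in a silently infected worker can be scored as symptomatic COVID-19

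*Combined protocol and SAP*

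**What the plan says.** The combined protocol and SAP states the primary objective as efficacy "in preventing symptomatic COVID-19 infections", and the Primary Endpoint entry gives "a decrease in symptomatic COVID infections from 15% to 5% in the treatment arm". The Sample size entry uses the same outcome: "Sample size based on a projection that 15% of healthcare workers will develop symptomatic COVID-19 illness".

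The Statistical analysis section names three sources for COVID disease status: "medical records review for severe hospitalized patients"; "self-reported history of viral illness with serological confirmation of anti-COVID status"; and antibody status. It does not say which of them makes a primary case. It then words the outcome without the symptomatic qualifier: "The primary end point, the percentage of patients with COVID infection at study end".

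GI effects of CQ are foreseen. Treatment Description says "A dose of 250 mg daily will be allowed for severe GI intolerance", and the third secondary endpoint is "Percent of patients with GI intolerance". Severe GI intolerance is also listed under Study Stopping Rules. No rule says whether a GI upset may be reported as a viral illness.

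**The concern.** Seroconversion is a separate secondary endpoint, so the plan itself distinguishes infection from symptomatic disease. For a worker who is not hospitalised, only the illness criterion separates the two, and that criterion is whatever the participant calls a viral illness. Positive serology shows that infection occurred at some time. It does not show that the reported illness was that infection. A cold in one month and a silent seroconversion in another satisfy the wording.

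If such errors are equally common among silently infected workers in both arms, and CQ leaves silent infection unchanged, they add the same number of points to each arm and dilute the relative effect. If GI effects of CQ are also reported as viral illness, the extra false cases fall mainly on CQ and the error no longer balances. Identical bottles do not prevent this, because a blinded participant still has the symptoms and must guess their cause.

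**Working it through.** **The plan's own figure.** Inputs from Sample size and Statistical analysis: 15% vs 5%, two-sided alpha 0.05, 80% power, 10% dropout. The pooled-variance formula for two proportions gives 141 per arm, or 160 with continuity correction. Allowing for dropout, 160 / 0.9 = 178 or 160 × 1.1 = 176, close to the stated 175. So the planned number reproduces. With 10% lost, 175 × 0.9 = 157.5, taken as 157 evaluable per arm.

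**Reference power.** The exact power of the uncorrected chi-square test at 157 per arm, 15% vs 5%, is 86%. This unstratified test stands in for the planned Cochran–Mantel–Haenszel test.

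**Assumptions (none is in the documents).**
- a = asymptomatic seroconversion, 10% on placebo
- b = chance that such a worker reports an unrelated viral illness, 10–30%
- g = chance that a GI effect of CQ is reported as a viral illness, 0 or 10–20%

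**Formulas.** Placebo = 15% + a × b. CQ = 5% + a(CQ) × [1 − (1 − b)(1 − g)]. The bracket counts a worker with both a cold and a GI upset once.

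**Case 1: CQ leaves asymptomatic infection unchanged, a(CQ) = 10%.**

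| b | g | Placebo | CQ | Apparent reduction | Power |
|---|---|---|---|---|---|
| 10% | 0 | 16.0% | 6.0% | 62.5% | 83% |
| 30% | 0 | 18.0% | 8.0% | 56% | 76% |
| 10% | 10% | 16.0% | 6.9% | 57% | 73% |
| 10% | 20% | 16.0% | 7.8% | 51% | 62% |
| 30% | 10% | 18.0% | 8.7% | 52% | 69% |
| 30% | 20% | 18.0% | 9.4% | 48% | 61% |

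For the last row, 1 − 0.7 × 0.8 = 0.44, so CQ = 5% + 10% × 0.44 = 9.4%.

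**Case 2: CQ cuts asymptomatic infection by two thirds, a(CQ) = 3.3%.** With g = 0 the apparent reduction stays at 67%; for example, 18% vs 5% + 3.3% × 0.3 = 6%. With g = 10–20%, simply adding b + g gives CQ rates of 5.7–6.7%, an apparent reduction of 62.5–65% and power of 83–90%. That sum slightly overstates the loss. Counting overlaps once moves each range by no more than about one point.

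**No true effect, a = 10% in both arms.** CQ minus placebo = 10% × (1 − b) × g. This runs from 10% × 0.7 × 0.1 = 0.7 points to 10% × 0.9 × 0.2 = 1.8 points. It is zero if g = 0.

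**The case against.** The strongest objection concerns size. Holding asymptomatic infection at 10% in both arms implies total seroconversion of 15 + 10 = 25% vs 5 + 10 = 15%, a 40% reduction. The plan projects a 67% fall in seroconversions, and its Rationale rests on reduced viral replication. On that projection (case 2) power is at worst about 3 points below the reference. This stands: the large losses belong to a scenario that the plan does not assume. The scenario remains possible, and the trial cannot know beforehand which case applies.

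Second, a reader might infer that GI effects of CQ will be scored as COVID-19. The documents do not support that. The value g is not the GI rate on CQ; it is the chance that a health care worker reports a drug effect as a viral illness. No document gives it, and GI intolerance has its own endpoint. A reader might also add b and g and arrive at 18% vs 10% with 54% power, but that counts some workers twice.

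Third, the direction is against CQ, so the error does not manufacture a benefit. This also stands, but missing a real effect is still a cost.

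Fourth, the analysis section calls the endpoint COVID infection. If that wording governed, every seropositive worker would count and self-report would not matter. This is a real inconsistency and has to be settled first. It does not remove the point, because the objective, the primary endpoint and the sample size all specify symptomatic illness, and that outcome needs an illness definition.

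**Conclusion.** The concern holds in limited form. Following the stated rule, an unrelated illness in a worker with asymptomatic infection can be scored as symptomatic COVID-19, and serology does not prevent it. Only workers with positive serology are affected, and severe hospitalised cases come from records.

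The size is an assumption throughout. The unrelated-illness limb alone moves power from 86% to 76–83% if CQ does not affect asymptomatic infection, so the upper end of the assumed illness rate falls below the 80% target without any GI argument. The 61–73% range needs a GI misreporting rate that nothing in the documents supports. Under the plan's own projection for seroconversion the effect is small. The documents do not support reading this as a demonstrated loss of power or a demonstrated excess on CQ. It is a loose primary case rule that should be tightened because the repair is cheap.

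**What to change.** 1. Reconcile the COVID infection wording in Statistical analysis with the symptomatic endpoint in the objective and Primary Endpoint entries, and state which ascertainment source makes a primary case.
2. Define a non-hospitalised symptomatic case as an illness after randomisation that meets a pre-listed set of COVID-19 symptoms, with a recorded onset date, in a worker who was antibody-negative at the draw before onset and positive at the next draw after it. Classify cases blind to arm.
3. State the antibody draw times, including one at baseline. The document gives none, and the rule depends on them.
4. Report the broad self-report definition as a sensitivity analysis, and the handling of GI-only illness as another. Excluding GI-only illness outright is debatable, since it could discard true cases.

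The cost is a short symptom and date record at follow-up visits, any antibody draw not already planned, and a somewhat lower counted event rate. The 175 per group need not change on this account alone. If draws coincide with the stated 2- and 3-month visits, the window may span up to two months, so some unrelated illnesses will still qualify. The symptom list must do part of the work.

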### **Rationale:**

We generally consider hydroxychloroquine and chloroquine as being effective in lupus, in part due to inhibition of type I interferon (considered our innate first line defense antiviral response), which has often raised concern about susceptibility to viral infection. However, data are accumulating at a very rapid rate that there may be a paradox. By raising endosomal pH (one of the mechanisms that leads to decreased TLR ligation and decreased IFN) COVID viral replication itself is decreased. Since acidification is crucial for endosome maturation and function, Liu and colleagues suggest that endosome maturation could be blocked at intermediate stages of endocytosis, which would then result in decreased transport of virions to the ultimate releasing site. A study by Goa et al. suggests that chloroquine has efficacy against the associated pneumonia in multicenter clinical trials conducted in China. Additionally, there have been two other small trials that raise more questions than provide definitive answers to the question of hydroxychloroquine efficacy in COVID-19. Specifically, the study by Gautret et al. was a single arm protocol in which 20 confirmed COVID-19 patients were given 600mg of hydroxychloroquine daily (and in some cases azithromycin) and their viral load in nasopharyngeal swabs was tested. Six patients were asymptomatic, 22 had upper respiratory tract infection symptoms and eight had lower respiratory tract infection symptoms. A significant reduction of viral carriage was reported. Of note, levels of HCQ were in accord or lower than those seen in our lupus patients prescribed 5mg/kg. The heterogeneity of the patients included, selection of the control population, high rate of lost to follow-up and handling of missing

observations raise concerns about their conclusions. The other trial is a 30 patient, placebo-controlled study of hydroxychloroquine in patients with relatively mild COVID-19 infections, using 400 mg of HCQ daily, did not show any differences between drug and placebo groups in viral clearance, duration of hospitalization, and radiological progression of COVID-19 pneumonia. CQ and HCQ have been used interchangeably in the treatment and prophylaxis of malaria as well as the treatment of SLE. The current study proposes to evaluate the efficacy of CQ in preventing COVID-19 infections.

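### Illness outside hospital counts only if antibody confirms it, with no virus test accepted and no draw timing given, so illness shortly before the last blood draw is missed

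*Combined protocol and SAP*

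**What the plan says.** The Primary Objective is the efficacy of CQ "in preventing symptomatic COVID-19 infections".

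The Statistical analysis section names three sources of COVID status. The first is record review, limited to severe hospitalised patients. The other two are "self-reported history of viral illness with serological confirmation of anti-COVID status, and anti-COVID antibody status". It then describes what is tested: "The primary end point, the percentage of patients with COVID infection at study end". Whether that means symptomatic illness or any infection, a participant who was not hospitalised reaches case status only through antibody.

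The Secondary Objectives use the same marker, for "preventing any infection as defined by seroconversion to positive anti-COVID antibody status".

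On timing, Study Duration gives treatment for 2-3 months or until exposure is negligible, and "2 month follow up visit, 3 month follow up visit". No blood draw is tied to either visit. No interval between illness and draw, convalescent sample or assay performance is stated.

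The Rationale describes raised endosomal pH as "one of the mechanisms that leads to decreased TLR ligation and decreased IFN", and says that viral replication is decreased. It does not discuss antibody production.

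**The concern.** Antibody becomes detectable some time after infection. A participant who falls ill close to the last draw may still be antibody negative, and under the stated rule is then a non-case. A positive virus test in that person's record would not change this, because it is not among the listed sources. In a trial of 2-3 months, a lag of a few weeks is a sizeable part of the counting period. What is at stake is primary events, and so power.

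A second, separate matter is that one immune marker decides nearly all non-hospitalised primary events and all of the seroconversion secondary. If confirmation worked less well in one arm, both endpoints would move the same way, and the plan specifies no independent confirmation for cases outside hospital.

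**Working it through.** **Inputs from the documents.** 15% versus 5%, 175 per group, 10% dropout, 80% power, two-tailed (Sample size); alpha 0.05 (Statistical analysis); 2-3 months (Study Duration). Evaluable per arm: 175 × 0.90 = 157.5, taken as 157.

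**Inputs not in the documents (assumed).** Lag from illness to detectable antibody of 1, 2 or 3 weeks; constant hazard; last draw at the end of a counting window of 8.7 weeks (2 months) or 13 weeks (3 months); every case dependent on antibody; 15% and 5% are true symptomatic rates.

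**The plan's own figure.** For two proportions, n = [1.96√(2 × 0.10 × 0.90) + 0.842√(0.15 × 0.85 + 0.05 × 0.95)]² / 0.10² = 141 per group. With continuity correction it is 160. Allowing for 10% dropout gives 160 / 0.90 = 178 or 160 × 1.10 = 176, within 2% of 175. The sample size is not in error.

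**Late cases.** The fraction missed is f = lag / window. Scaling each arm's hazard by (1 − f), the counted rate is 1 − (1 − p)^(1 − f). Power is the exact probability, over two binomials with 157 per arm, that an uncorrected chi-square test is significant at two-sided 0.05. This is unstratified, as an approximation to the planned stratified test. With nothing missed it is 86%.

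| Window | Lag | f | Counted, placebo | Counted, CQ | Power |
|---|---|---|---|---|---|
| 8.7 weeks | 1 week | 11% | 13.4% | 4.4% | 82% |
| 8.7 weeks | 2 weeks | 23% | 11.8% | 3.9% | 76% |
| 8.7 weeks | 3 weeks | 34% | 10.1% | 3.3% | 69% |
| 13 weeks | 1 week | 8% | 13.9% | 4.6% | 83% |
| 13 weeks | 2 weeks | 15% | 12.8% | 4.2% | 80% |
| 13 weeks | 3 weeks | 23% | 11.8% | 3.9% | 76% |

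The risk ratio stays between 0.327 and 0.332, against 0.333 with nothing missed. Equal loss therefore hardly moves the estimate.

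As a cross-check, a normal approximation with rates scaled directly by (1 − f) over 60 or 90 days starts at 84%. For lags of 7, 14 and 21 days it falls to 79%, 73% and 65% (60 days) or 81%, 77% and 73% (90 days), which is the same pattern.

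**Unequal confirmation (illustration only).** Take a true rate of 15% in both arms and assumed antibody sensitivity of 95% on placebo. The counted placebo rate is 0.15 × 0.95 = 14.25%.

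| Sensitivity on CQ | Counted, CQ | Apparent reduction | Significant, either direction |
|---|---|---|---|
| 95% | 14.25% | 0% | 4.9% |
| 90% | 13.5% | 5% | 5.4% |
| 80% | 12.0% | 16% | 9% |
| 70% | 10.5% | 26% | 17% |

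A small difference has almost no effect; only a large one matters. No sensitivity for either arm is given in the documents.

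**The case against.** **The text lists sources and does not say that a positive virus test is disregarded.** The Study Stopping Rules also make symptomatic COVID-19 infection a trigger for a hold, which implies that cases are recognised during the trial. This stands in part. However, the stopping rules give no method of recognition, and for illness outside hospital the Statistical analysis section requires serology. As written, that is a rule and not merely silence.

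**The draw date and lag are assumed.** This is correct. If treatment lasts 2 months and blood is drawn at the 3-month visit, about a month remains for antibody to appear. The loss then shrinks or vanishes for illness during treatment, though illness just before that draw would still be missed if it counts.

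**The power loss is an upper reading.** This also stands. Hospitalised cases do not depend on antibody: if, say, 20% of cases came through hospital records (an assumption), the worst row becomes f = 0.345 × 0.80 = 27.6% and power is 73%. The Sample size paragraph reads "Sample size based on a projection that 15% of healthcare workers will develop symptomatic COVID-19 illness"; if that already means antibody-confirmed illness, no power is lost. Power also stays at about 80% or above in three of the six rows.

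**A reader might infer that the sponsor's rationale predicts weaker antibody responses on CQ, so that the primary result is biased in its favour.** The documents do not support this. The Rationale covers type I interferon (which it calls innate), TLR ligation and endosomal pH; the step to antibody production is extrapolation. Nor would such an effect be wholly invisible. Severe hospitalised cases are found through records, severe illness is a co-primary endpoint, and self-reported illness without antibody could be tabulated by arm. These checks are weak, and the plan does not ask for the tabulation, but they exist.

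**Conclusion.** The point holds as a weakness in the case definition. Outside severe hospitalised cases, a symptomatic illness counts only with antibody, no virus test is an alternative, and the draw is not timed relative to illness. Illness shortly before the last draw is missed whenever that draw falls.

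The size depends on the assumptions listed above: about 8-34% of antibody-dependent cases lost, and power down from 86% to between 83% and 69%. The loss is smaller if hospitalised cases are a material share, if the draw follows the counting window, or if the 15% projection already refers to antibody-confirmed illness. It is a loss of power, with no material bias in the risk ratio when the lag is equal in both arms.

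Reliance on one immune marker for the primary endpoint and the seroconversion secondary is a reason to build in a check. It does not show that the trial is biased towards CQ.

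**What to change.** Change the case definition in the Statistical analysis section so that a symptomatic illness in the counting window is confirmed by either a positive SARS-CoV-2 virus test in the participant's available records or seroconversion, adjudicated blind to arm. State the counting window and the timing of the last draw, so that the rule can be applied.

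Add two sensitivity analyses by arm: virus-test-confirmed cases, and symptomatic illness without antibody confirmation. Disagreement between these and the antibody-based result would flag differential confirmation.

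Do not add a rule excluding antibody-confirmed illness with onset in the last 3 weeks before the draw. It would discard events that are already confirmed and make certain the loss it is meant to address.

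The cost is wording, a data field and more record review; no new test is required. The remedy is imperfect. It recovers only late cases that happened to be tested, testing outside the trial will not be uniform, and a virus test could itself be affected by a drug that lowers viral replication, as the Rationale proposes. That is why either form of confirmation should count and both should be shown by arm.

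### The primary test is tied to COVID infection with no symptom requirement, while the stated primary endpoint and the sample size rest on symptomatic COVID-19

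*Combined protocol and SAP*

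**What the plan says.** The synopsis sections are consistent with one another. The Primary Objective concerns efficacy "in preventing symptomatic COVID-19 infections", and Study Design repeats it. The Primary Endpoint is "a decrease in symptomatic COVID infections from 15% to 5% in the treatment arm". Sample size takes its 175 per group from the same two rates.

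Infection regardless of symptoms ranks lower. Secondary Objectives describes "preventing any infection as defined by seroconversion to positive anti-COVID antibody status", and the first item under Secondary Endpoints is "Decrease by 67% in number of sero-conversions in at risk healthcare workers". Sample size adds: "The trial is not powered on any secondary outcomes or interim analyses".

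The Statistical analysis section is the only place that assigns a test to the primary endpoint, and it reads: "The primary end point, the percentage of patients with COVID infection at study end, will be compared". The comparison is a CMH test stratified by age and exposure level. The same section gives three sources for COVID disease status: records review for severe hospitalised patients, then "self-reported history of viral illness with serological confirmation of anti-COVID status, and anti-COVID antibody status". Other categorical outcomes fall under a general provision ("Counts and percentages will be calculated for categorical variables and compared using") for chi-square or Fisher's exact tests.

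**The concern.** The protocol itself distinguishes symptomatic infection from any infection, and that distinction separates the primary from the secondary question. The sentence defining the primary test drops the qualifier. Because antibody status stands as a source of its own, separate from illness confirmed by serology, a participant who seroconverts without symptoms could be counted as a primary event. Symptomatic illness would then have no named test beyond the general chi-square or Fisher provision.

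At stake is what the trial may conclude. A drug that suppresses symptoms without preventing infection would show no difference on infection. A positive result on infection would not by itself establish prevention of symptomatic illness. Since the document supports both definitions, either result could later be put forward as primary.

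**Working it through.** **1. Which endpoint the sample size belongs to.** Inputs from Sample size: 15% versus 5%, 80% power, two-tailed, 10% dropout. Alpha 0.05 is from Statistical analysis, and 1:1 allocation is from the randomisation text in the ECG section.

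- Without continuity correction: n = [1.96·√(2·0.10·0.90) + 0.8416·√(0.15·0.85 + 0.05·0.95)]² / 0.10² = 140.1, so 141 per arm.
- With continuity correction: n = (140.1/4)·[1 + √(1 + 4/(140.1·0.10))]² = 159.5, so 160 per arm.
- Dropout: 160/0.9 = 177.8, so 178; or 160 × 1.1 = 176.

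The stated 175 is reproduced to within 3 participants, using the symptomatic rates. The documents give no control rate for any infection, so no such calculation can be made for the outcome named in Statistical analysis.

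**2. Power under each definition.** Evaluable n = 175 × 0.9 = 157.5, taken as 157 per arm. The asymptomatic placebo rate is assumed at 5%, 10% or 15%, so any infection on placebo is 20%, 25% or 30%. Power comes from exact enumeration of two binomials with an unstratified Pearson chi-square test at two-sided 0.05, as an approximation to the CMH test.

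| Assumed effect of chloroquine | Any infection, placebo vs chloroquine | Power on any infection |
|---|---|---|
| Asymptomatic infection unchanged | 20 vs 10, 25 vs 15, 30 vs 20% | 0.705, 0.607, 0.538 |
| All infection cut by 67% | 20 vs 6.7, 25 vs 8.3, 30 vs 10% | 0.948, 0.983, 0.996 |
| Symptomatic turned into asymptomatic only | 20 vs 20, 25 vs 25, 30 vs 30% | about 0.05 |

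Power on the symptomatic endpoint (15% versus 5%) is 0.861 throughout.

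**3. How often the two definitions disagree.** Simulation of 400,000 trials per scenario with symptomatic rates of 15% and 5%. The table gives the probability that one test is significant and the other is not, at asymptomatic placebo rates of 5%, 10% and 15%.

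| Assumed effect | 5% | 10% | 15% |
|---|---|---|---|
| Asymptomatic infection unchanged | 0.202 | 0.304 | 0.374 |
| All infection cut by 67% | 0.102 | 0.127 | 0.135 |
| Symptomatic turned into asymptomatic only | 0.848 | 0.842 | 0.839 |

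**4. Cost of an open choice.** With no drug effect (15% symptomatic in both arms, and 5%, 10% or 15% asymptomatic in both), the probability that at least one of the two tests is significant is 0.075, 0.082 or 0.085, against a nominal 0.05.

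**The case against.** The strongest reply is that this is loose wording, not a second definition. The synopsis gives symptomatic illness as the target four times, so the phrase in Statistical analysis may simply refer back to it. The Rationale also closes by speaking of preventing COVID-19 infections without the qualifier. The three ascertainment sources can be matched to the severe (co-primary), symptomatic (primary) and seroconversion (secondary) endpoints. The secondary endpoint needs antibody status whatever the primary is, so listing it proves little about what the CMH test counts. That benign reading is possible, but no section states the matching or limits the test to symptomatic cases. An analyst working from the text cannot tell which participants are primary events.

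The reply also has force on size:

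- The 7.5–8.5% false-positive rate assumes a free choice that no section grants. It is a worst case.
- The 84–85% disagreement needs a pure shift from symptomatic to asymptomatic infection, which the documents do not anticipate.
- Under the 67% cut in seroconversions that Secondary Endpoints does anticipate, disagreement is 10–14%. Nearly all of it is the infection test succeeding where the symptomatic test fails (about 0.094 of 0.101 at a 5% asymptomatic rate, 0.125 of 0.127 at 10%).

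A loss of power is therefore not certain. The mismatch remains whichever way power moves.

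**Conclusion.** The concern holds and must be fixed before unblinding. The conflict is one of definition and can be seen without calculation: the only sentence that assigns the primary test describes the outcome that the rest of the protocol ranks as secondary. Compared with 86% for symptomatic illness, power for the literal reading runs from about 5% to 99.6%, and the two definitions disagree in roughly 10% to 85% of trials. These ranges rest on assumed asymptomatic rates of 5–15%, 157 evaluable per arm and an unstratified test in place of the CMH test. The main harm is that the confirmatory test may not address the primary objective and that the choice of primary result is left open.

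**What to change.** In Statistical analysis, define the outcome of the stratified CMH test as symptomatic COVID-19 between randomisation and study end, meaning either self-reported viral illness with serological confirmation or hospitalised COVID-19 on records review. State that antibody positivity without symptoms counts only toward the secondary seroconversion endpoint, and that hospitalised cases also continue to count toward the co-primary severe-illness endpoint.

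The cost is a wording change plus asking participants when the reported illness occurred. The 175 per group already rests on this endpoint, so sample size, visits and assays are not affected by this correction. Serology alone cannot show that an infection began after randomisation; that is a separate question, which this change does not settle.

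If the sponsor does intend any infection to be primary, the objective, the endpoint and the sample size would all have to be redone, with a stated control rate for infection.
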